All patients in Part 1 of the study (i.e., Cohorts 1, 2, 3a-b, and 4a-d) will follow similar visit and assessments schedules. Selected assessments () will be optional for all enrolled patients at Sponsor-qualified sites. Other assessments (e.g., ABPM,) conducted for Cohorts 1 and 2 will not be conducted for patients in Cohorts 3 and 4. Following randomization, patients will be assessed in person during treatment at Weeks 1, 2, 4, 8, 12, and 16 and by telephone contact on Days 3, 10, and 21. Patients enrolling in Cohorts 3 and 4 will have additional assessments in person at Week 6 and additional telephone contact on Days 31, 38, and 49. Patients who do not enter Part 2 of the study (i.e., the extension period), either because they have discontinued taking study drug during Part 1 or have completed the 16-week treatment period as planned but chosen not to continue to Part 2 of the study, will complete an end-of-treatment visit when patient ends study drug. In addition a follow-up visit should occur four weeks after the date of administration of the last dose of study drug.

Part 2 (extension period):

Patients who discontinue treatment prematurely in study Part 1 are not eligible to continue into study Part 2. All patients from Part 1 who complete the 16-week treatment period as planned will be eligible to continue directly into the extension period to evaluate the intermediate and long-term safety and efficacy of bardoxolone methyl. Day 1 of the extension period will be the same as the Week 16 visit for the treatment period.

Cohort 1 and Cohort 2 patients randomized to placebo in Part 1 of the study will be assigned to receive bardoxolone methyl at their group-specific dose in the extension period. Patients enrolled in Cohorts 1 and 2 may dose titrate to the 10 mg dose or de-escalate at scheduled or unscheduled visits. However, patients who dose escalate must have a telephone call 1 week after

dose escalation and an unscheduled office visit or a home health visit 2 weeks (± 3 days) after dose escalation to collect clinical chemistry, BNP, and NT-Pro BNP.

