^b Study Day 1 is the day of administration of the first dose. **On Study Day 1, all procedures should be performed before study drug administration.**

^c Under the delegation of the Investigator and following Sponsor prior approval for each visit, a patient may be seen by a home health professional, qualified by documented training to perform study-specific procedures.

^d Patients who discontinue from the study prior to the Week 16 study visit will need to be brought back for all early termination assessments (i.e., both an end-of-treatment visit and then a follow-up visit 4 weeks after the date of administration of the last dose of study drug). Patients should complete the end-of-treatment procedures, including the 6MWT, prior to any adjustments being made to their PAH treatment regimen.

^e Screen A and Screen B eligibility procedures do not need to be repeated on Day 1; however, a review of any changes in eligibility criteria should be evaluated prior to Day 1 procedures, and a urine pregnancy test should be performed for WOCBP.

^f Weights taken at home by the patient will begin on Day 2 and should be taken daily for the first 4 weeks and weekly thereafter, preferably at the same time each day and must be recorded in a diary and reviewed with the coordinator during telephone contacts and office visits.

^g Physical examinations must be performed by a qualified physician, physician's assistant, or registered nurse practitioner.

^h If clinical worsening is suspected, further clinical evaluations may be required per Section 9.10.32.

ⁱ If the visit is completed by home health professional, a limited physical assessment directed to assess for fluid retention and clinical worsening will be performed under the delegation of the Investigator

^j A serum pregnancy test will be performed at Screen A for WOCBP or at any point in time if a pregnancy is suspected. All other pregnancy assessments will be urine pregnancy tests. Additional pregnancy assessments will be performed more frequently if required by local law or requested by local regulatory authorities or IRBs/ECs.

^k AE assessments on Day 1 should be done following study drug administration.

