^l Patients must be allowed to rest for a minimum period of one hour following arrival at the clinic and prior to collecting this blood sample. Similarly, this sample must be taken prior to the 6MWT. This sample should be taken with the patient in the same position at all appropriate visits, e.g., sitting or semi-recumbent.

^m Tests for hepatitis B and hepatitis C. If the initial hepatitis C result is positive, then the patient will need to return for an unscheduled HCV RNA assessment to determine if the virus is present at the current time. If the results of this test are negative, the patient may continue in the screening process.

ⁿ The 6-minute walk test must be performed on two separate days prior to randomization and on 2 separate days within the Week 4 and Week 16 3-day window.

^o Day 1 ECHO, [REDACTED] can be performed anytime after the patient qualifies (completed Screen A and Screen B) for the study and prior to study drug administration. The Week 4 and 16 ECHO, [REDACTED] assessments must occur within the visit window (+/- 3 days); however, they can be performed on different days than the other visit assessments. [REDACTED]

^p Echocardiography (ECHO) within 60 days prior to Day 1 may be used to determine eligibility [REDACTED]

[figure not shown]

^q [REDACTED]

- ^s Prior to randomization, the patient must have a qualified 24-hour ABPM assessment. If first 24-hour assessment is not qualified, one re-test may be performed prior to randomization. If the second test result does not qualify the patient will be considered a screen failure.
- ^t Pulmonary function tests within 90 days prior to Day 1 may be used to determine eligibility. Right heart catheterization within 36 months prior to Day 1 may be used to determine eligibility.
- ^u Completed immediately following the completion of the 6MWT.
- ^v [REDACTED]
- ^w If clinical worsening is suspected, perform unscheduled functional class assessment.
- ^x Blood samples for PK analysis should be drawn just prior to (0 hour) and after (2 and 4 hours) dose administration for this visit. Patients should be instructed to not take their study drug prior to coming to the clinic at Week 4.

Abbreviations: ECG = electrocardiogram, ECHO = echocardiogram, PK = pharmacokinetic, s = serum, u = urine, WOCBP = women of child-bearing potential, [REDACTED]

[REDACTED] 6MWT = 6-minute walk test

Table 4: Part 1: Schedule of Assessments for Patients in Cohort 3 and Cohort 4 (PH-ILD Cohort)

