- ^j Patients must be allowed to rest for a minimum period of one hour following arrival at the clinic and prior to collecting this blood sample. Similarly, this sample must be taken prior to the 6MWT. This sample should be taken with the patient in the same position at all appropriate visits, e.g., sitting or semi-recumbent.
- ^k Tests for hepatitis B and hepatitis C. If the initial hepatitis C result is positive, then the patient will need to return for an unscheduled HCV RNA assessment to determine if the virus is present at the current time. If the results of this test are negative, the patient may continue in the screening process.
- ^l The 6-minute walk test on Day 1 is used to confirm eligibility and must be performed prior to randomization.
- ^m The 6-minute walk test must be performed on 2 separate days within the Week 16 3-day window.
- ⁿ Echocardiography (ECHO) within 60 days prior to Day 1 may be used to determine eligibility

[REDACTED]

- ^r All patients must have PFTs assessed within 90 days prior to Day 1 to determine eligibility.

[REDACTED]

- ^u If clinical worsening is suspected, perform unscheduled functional class assessment.

- ^v Blood samples for PK analysis should be drawn just prior to (0 hour) and after (2 and 4 hours) dose administration for this visit. Patients should be instructed to not take their study drug prior to coming to the clinic at Week 4.

[REDACTED]

Abbreviations: ECG = electrocardiogram, PK = pharmacokinetic, s = serum, u = urine, WOCBP = women of child-bearing potential, [REDACTED]

6MWT = 6-minute walk test,

F/U = Follow-up

Table 5: Part 2: Extension Schedule of Assessments for Patients in Cohorts 1 and 2

Assessment \ Study Week	Week 16 ^a (Day 1) (±3 days)	Week 17 (Phone) (±1 day)	Week 18 ^b (±3 days)	Week 19 (Phone) (±1 day)	Week 20 (±3 days)	Week 32 (± 5 days)	Week 56 and Every 24 Weeks Thereafter (±5 days) ^c	End of Treatment Visit ^d (± 5 days)	Follow-up ^d (± 5 days)
Concomitant medications		X	X	X	X	X	X	X	X
Weight in clinic			X		X	X	X	X	X
Weight at home ^e		X	X	X	X	X	X		
Dispense weight diary	X		X		X	X	X		
Collect/Review weight diary		X	X	X	X	X	X	X	
ECG						X		X	X
Vital sign measurements			X		X	X	X	X	X
Physical exam/clinical worsening assessment ^f			X ^g		X	X	X	X	X
Urine Pregnancy test for WOCBP ^h						X	X	X	X
Study drug administration	X	----- X -----							
Dispense study drug	X				X	X	X		
Collect study drug					X	X	X	X	
Telephone contact ⁱ		X		X					
Adverse event collection		X	X	X	X	X	X	X	X

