6. If a patient is on chronic oxygen therapy, oxygen should be given at their standard rate or as directed by a physician or a protocol.

Reasons for immediately stopping a 6MWT include the following: (1) chest pain, (2) intolerable dyspnea, (3) leg cramps, (4) staggering, (5) diaphoresis, and (6) pale or ashen appearance.

Technicians must be trained to recognize these problems and the appropriate responses. If a test is stopped for any of these reasons, the patient should sit or lie supine as appropriate depending on the severity of the event and the technician's assessment of the severity of the event and the risk of syncope. The following should be obtained based on the judgment of the technician: BP, pulse rate, oxygen saturation, and a physician evaluation. Oxygen should be administered as appropriate.

TECHNICAL ASPECTS OF THE 6MWT**Location**

The 6MWT should be performed indoors, along a long, flat, straight, enclosed corridor with a hard surface that is seldom traveled. The walking course must be 15-30m in length. An approximate 49 to 98-ft hallway is, therefore, required. The length of the corridor should be marked every 3 meters. The turnaround points should be marked with a cone (such as an orange

traffic cone). A starting line, which marks the beginning and end of each lap, should be marked on the floor using brightly colored tape.

Rationale

A shorter corridor requires patients to take more time to reverse directions more often, reducing the 6MWT.

REQUIRED EQUIPMENT

1. Countdown timer (or stopwatch)
2. Mechanical lap counter
3. Two small cones to mark the turnaround points
4. A chair that can be easily moved along the walking course
5. Worksheets on a clipboard
6. A source of oxygen
7. Sphygmomanometer
8. Telephone
9. Automated electronic defibrillator

PATIENT PREPARATION

1. Comfortable clothing should be worn.
2. Appropriate shoes for walking should be worn. A notation should be made in the patient's source documentation of which shoes the patient wore for the first test. Prior to each clinic visit the patient should be called/reminded to ensure they wear this same pair of shoes.
3. Patients should use their usual walking aids during the test (cane, walker, etc.). NOTE – if a patient uses a walking aid for the first test this same aide should be used during all subsequent test whether needed or not.
4. The patient's usual medical regimen should be continued. The patient should continue to take doses of study drug prior to the test.

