### 3.3 Analysis of Treatment Group Comparability

Demographic information (age, sex, ethnicity, race), baseline characteristics (baseline BMI, weight) and baseline disease characteristics (including PAH classification and details, time since diagnosis, baseline PAH concomitant medications, thromboembolic disease assessment, pulmonary function testing, oxygen use during 6MWTs and available baseline right heart catheterization data) will be summarized by treatment arm for all randomized patients.

Descriptive baseline summaries of continuous data will present the group mean, standard deviation, median, minima, and maxima. Descriptive summaries of discrete data will present the category counts as frequencies and percentages.

Unless otherwise stated, the baseline value of any variable will be defined as the last available value recorded prior to the first administration of bardoxolone methyl/placebo. Missing values will not be imputed, unless otherwise noted, and will be tabulated as missing.

### 3.4 Analysis of Part 1

Part 1 data will be analyzed using the analysis populations defined in [Section 3.1](#). Separate analyses will be performed by each cohort. Part 1 analyses will only include data from the placebo controlled portion of the study. If a subject does not complete Part 1, or chooses not to enter Part 2, then all their data will be used in Part 1. If a subject enters Part 2, then all data up to and including the Week 16 visit will be included in Part 1.

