### 3.4.4.1 Primary Efficacy Endpoint

The primary measure of efficacy is the overall treatment effect across Week 4, Week 8, Week 12, and Week 16 for change from baseline in exercise capacity, as measured by the 6MWD, for bardoxolone methyl compared to placebo. The difference in mean overall change from baseline through Week 16 (active – placebo) will be used to assess the effect of bardoxolone methyl on 6MWD in patients with PAH. A lower 6MWD reflects greater PAH severity thus, a positive change from baseline suggests an improvement.

As supportive analysis to the primary endpoint, the mean change from baseline and treatment differences will be estimated for each visit. The actual values and changes from baseline in 6MWD will be summarized using descriptive statistics at each scheduled visit. Walk distances collected at any duration other than 6 minutes will not be included in the analysis of 6MWD unless the reason for not walking 6 minutes is one listed in the ATS guidelines as a reason for stopping the test immediately (i.e., chest pain, intolerable dyspnea, leg cramps, staggering, diaphoresis, and pale or ashen appearance).

Baseline for 6MWD will be the average of scheduled predose assessments (e.g., Screen A and Day 1) collected prior to the first administration of study drug. Similarly, two 6MWD measurements collected at Week 4 and again at Week 16. Multiple measures are within the Week 4 and Week 16 visits, and the 6MWD value used as at these visits is the calculated average within these visits.

The mean overall treatment effect across all visits for change from baseline in 6MWD will be estimated and compared with placebo through 16 weeks of treatment by mixed-model repeated measures (MMRM), with treatment group, visit, and the interaction between treatment and visit as fixed factors. Visits at Weeks 4, 8, 12, and 16 will be used. A compound symmetry covariance matrix will be assumed. Point estimates and 95% confidence intervals for the mean change from baseline for each treatment as well as the treatment difference (active-placebo) will be provided overall and at each protocol scheduled timepoint.

Separate mixed models will be used to compare (1) pooled bardoxolone methyl doses with placebo and (2) individual dose levels with placebo. The first model contains two treatment groups with data at four timepoints. Example SAS code to obtain estimated treatment differences is provided below.

```
Proc Mixed data=x order=data;

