### 3.5.4 Efficacy

Efficacy analyses described in Section 3.4.3 will not be performed on available data from Part 2. Instead, 6MWD will be summarized using descriptive statistics only (include 95% confidence interval for change from baseline at each visit) using the Part 2 treatment groups (BARD, PBO-BARD) Patients randomized to placebo and converted to bardoxolone methyl in Part 2 should use the Week 16 eGFR value as baseline. If the Week 16 eGFR lab collection occurs after the date and time of first dose at Week 16, then the closest value prior to Week 16 should be used as baseline for patients randomized to placebo and converted to bardoxolone methyl. No inferential statistics will be provided for Part 2 data and missing 6MWD will not be imputed in Part 2.

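### A placebo patient's second Week 16 walk can follow the first Part 2 dose and still count as placebo data, because neither document orders the two events for 6MWD

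*Protocol*

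**What the plan says.** **Timing of the walks.** For Cohorts 3 and 4, Table 4 footnote m states: "The 6-minute walk test must be performed on 2 separate days within the Week 16 3-day window". For Cohorts 1 and 2, Table 3 footnote n requires walks "on 2 separate days within the Week 4 and Week 16 3-day window". Week 16 is Day 112 ±3.

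**Start of Part 2.** Protocol 7.1 states: "Day 1 of the extension period will be the same as the Week 16 visit for the treatment period". Protocol 10.2 starts the extension with the Week 16 dispensing, and Tables 5 and 6 mark Part 2 drug as both dispensed and administered at that visit. Placebo patients move to bardoxolone at this point (Protocol 7.1 and 7.3).

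**Order of assessments and dosing.** Tables 3 and 4 say: "On Study Day 1, all procedures should be performed before study drug administration". Study Day 1 is defined there as the day of the first dose. Protocol 9.10 has a similar rule, also tied to the first dose of study drug. Tables 5 and 6 have no such rule for extension Day 1; they only refer the remaining Week 16 assessments back to Tables 3 and 4.

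**Analysis.** SAP 3.4 draws the line between Parts 1 and 2 by visit: "If a subject enters Part 2, then all data up to and including the Week 16 visit will be included in Part 1". On the repeated walks, SAP 3.4.4.1 says "the 6MWD value used as at these visits is the calculated average within these visits". SAP 3.7.2 uses scheduled walks whatever their study day. SAP 3.5.4 foresees the timing problem ("If the Week 16 eGFR lab collection occurs after the date and time of first dose at Week 16") but supplies a rule for the eGFR baseline only.

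**The concern.** A site can do the first walk at the Week 16 visit, dispense Part 2 drug, and bring the patient back for the second walk inside the window. No ordering rule in either document forbids this. A placebo patient handled this way does the second walk on bardoxolone, and the SAP counts it as placebo data.

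The arms are not affected equally. Patients randomized to bardoxolone in Cohorts 3 and 4 enter Part 2 on the dose they ended with, so nothing changes for them between the walks. An early drug effect on 6MWD would therefore enter the control arm's Week 16 value alone.

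Three uses are exposed:
- the Week 16 treatment difference, which SAP 1.10 keeps as an estimate because it was the original endpoint;
- the four-visit overall effect, which SAP 3.1.3 intends to use for powering later trials;
- the Part 2 change-from-Week-16 summaries (SAP Appendix B), which share the same reference value.

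The protocol does fix the order in comparable situations. The Day 1 walk precedes randomization, BNP precedes the walk, and the end-of-treatment walk precedes any change in PAH therapy (Table 4 footnotes l, j and d). The planned switch from placebo to active drug has no counterpart.

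**Working it through.** The plan states no figure on this point, so there is none to reproduce. The check is of sequence first, then size.

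**1. Possible exposure before the second walk.** The window runs from Day 112 − 3 = 109 to Day 112 + 3 = 115, so the walks can be 115 − 109 = 6 days apart. If Part 2 drug is first taken on the day of walk 1 and a dose is also taken before walk 2, that is up to 7 doses. This is the extreme corner of the window.

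**2. Placebo patients to whom the gap could apply, if they enter Part 2.**
- Cohorts 3 and 4, planned: 6 × 24 × 1/3 = 48.
- Cohorts 3 and 4, maximum: 6 × 72 × 1/3 = 144.
- Cohorts 1 and 2: (38 + 16) × 1/4 = 13.5, so about 13 or 14.

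**3. Weight of one walk.** Week 16 is the mean of two walks, so each has weight 1/2. The primary measure averages Weeks 4, 8, 12 and 16. With LOCF-completed data and the compound-symmetry model of SAP 3.4.4.1, a generalized least squares check confirmed that the overall difference equals the plain mean over the four visits. One Week 16 walk therefore has weight 1/2 × 1/4 = 1/8.

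**4. Shift in the treatment difference.** Let D be the full effect, taken as equal at all four visits; p the share of placebo patients whose second walk follows the switch; and g the share of D present by then. Neither p nor g is in the documents.
- Week 16: shift = p × g × D/2.
- Overall: shift = p × g × D/8.

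| p | g | Week 16 (share of D) | Overall (share of D) |
|---|---|---|---|
| 0.25 | 0.10 | 1.2% | 0.3% |
| 0.50 | 0.10 | 2.5% | 0.6% |
| 0.50 | 0.25 | 6.2% | 1.6% |
| 0.50 | 0.50 | 12.5% | 3.1% |
| 1.00 | 1.00 (ceiling) | 50% | 12.5% |

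**5. Does the SAP remove such a walk?** No. The second walk belongs to the Week 16 visit, so the cut in SAP 3.4 keeps it, SAP 3.4.4.1 averages it in, and SAP 3.7.2 sets no limit by study day. With a cut at the first Part 2 dose, the shift by this route would be zero.

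**The case against.** The best counter-argument is that the order is implicit. Part 2 is open only to patients who complete Part 1 as planned, both walks are Part 1 assessments, and Protocol 10.4 continues study drug through the Week 16 visits. The likely intent is therefore assessments first and Part 2 drug second. That is a fair reading of intent, but none of this text says the second walk precedes the first Part 2 dose. The Day 1 rule in Protocol 9.10 cannot fill the gap either: it is tied to the first dose of study drug, which a placebo patient took 16 weeks earlier.

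Other objections limit how far the point goes, and they stand:

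- **Direction.** A reader might infer that the bias must be toward zero. That needs an early benefit. Protocol 5.1.2 places the fluid-overload risk in the first three to four weeks of treatment (seen in Stage 4 CKD), so an early fall in 6MWD, and bias the other way, cannot be ruled out. In Cohorts 1 and 2, active patients may also change dose in Part 2.
- **Size.** A reader might apply g/2 and g/8 to the whole trial. Those figures describe one affected placebo patient; the trial-level shift also needs p.
- **Appendix 1.** Its line "The patient should continue to take doses of study drug prior to the test" might be read as sending patients to the second walk on Part 2 drug. It is a general instruction for every walk and says nothing about Part 2 supply.
- **Day 119.** SAP Table 2 (SAP 3.7.4) lets unscheduled walks count toward Week 16 up to Day 119. A reader might take this as a second open route, but the visit-based cut in SAP 3.4 points the other way. It is a conflict to reconcile.
- **ABPM.** The Week 16 recording, at least 24 hours long, has the same gap. It is a safety measure in Cohorts 1 and 2 only and does not enter 6MWD.
- **Use of the result.** SAP 1.5.2 rests the primary objective on the totality of data, and SAP 1.9 calls the study exploratory.

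**Conclusion.** The gap is real and the SAP does not close it. As written, a walk done on bardoxolone by a placebo patient would be analysed as placebo data, although the SAP already recognizes the same hazard for eGFR.

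The effect on the primary measure is probably small. With half the placebo patients affected and 10% to 50% of the full effect present, the shift is about 0.6% to 3.1% overall and 2.5% to 12.5% for the Week 16 difference. A low g is plausible: exposure is a matter of days, SAP 3.1.3 expects the effect over the first few weeks, and placebo patients in Cohorts 3 and 4 start Part 2 at 5 mg. The figures assume a constant effect across visits, two usable Week 16 walks, and no change in the active arm between them. The sign assumes that any early effect is a benefit.

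The documents do not show how often sites separate the walks with a Part 2 dose. They therefore do not support saying that the comparison is materially biased, only that the rules allow bias which could be avoided cheaply.

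**What to change.** **SAP 3.4, 3.4.4.1 and 3.7.2.** Exclude from Part 1 any 6MWD value dated after the first Part 2 dose and, for Cohorts 1 and 2, any ABPM reading after it. If only one Week 16 walk precedes that dose, use that walk alone as the Week 16 value. The eGFR rule in SAP 3.5.4 already relies on the date and time of that dose. A convention is needed for a same-day walk with no recorded clock time.

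**SAP 3.7.4, Table 2.** Reconcile the Day 119 limit with the cut in SAP 3.4 by ending the Week 16 window at the first Part 2 dose for patients who enter Part 2.

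**Protocol Tables 3 to 6.** Reconcile the two-day walk requirement with the start of Part 2 at the same visit, so that the order of the Week 16 assessments and the first Part 2 dispensing is stated. Dosing and drug supply between the walks are for the sponsor. Supply needs thought: Part 1 bottles hold 30 capsules, and Day 81 (earliest Week 12 visit) to Day 115 is 34 days.

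**Cost.** A few SAP sentences and a protocol clarification. A few patients would contribute one Week 16 walk instead of two, with slightly less precision. The SAP rule alone removes the bias by this route and changes no dose.
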